
3. Method for Assigning Subjects to Groups:

Eligible participants will complete a baseline survey and subsequently assigned in a 1:1 ratio using a stratified randomization by race and region into the Intervention or Attention-Control condition. Participants recruited nationally will be assigned to a fifth “region” and randomized in a 1:1 ratio to the Intervention or Attention-Control condition.

4. Administration of Surveys and/or Process:

Surveys: We will collect survey data via online self-completed surveys administered at baseline, and 3, 6, 9, and 12 months, with an additional 15 months survey for control participants. Each survey will last approximately 30 minutes. Participants will enter their own responses to questions directly into the survey on their personal computer, smartphone or tablet. Participants will access the surveys via their profile on their password protected study website account. A total of 6 surveys will be conducted, for a total follow-up period of 15 months. The small time frames between assessments will help us to respond quickly to retention concerns. In addition, we have planned our incentive schedule to reflect the time that participants must spend completing the surveys. Incentives for completing the baseline, the 12-month follow-up survey, and the 15-month follow-up survey (for participants initially randomized into the control condition) will be \$30 per assessment, whereas the 3, 6, and 9-month follow-ups will be \$25 each since they are shorter in length. These incentives are small enough to avoid coercion, yet sufficiently substantial to promote retention. In order for interventions to be evaluated as potential best evidence-based interventions through CDCs Prevention Synthesis Research activity, data must be available for at least a single follow-up time point for at least 70% of participants. As indicated below, a detailed retention plan for the study will draw on previously successful retention protocols to achieve at least an 80% retention rate for the first follow-up visit. Our experience has shown that successful retention has several key elements. First, it is critical to obtain accurate follow-up contact information. We will use best practices to retain participants (e.g., comprehensive locator information that includes participants' cell phone number, e-mail, Facebook and/ or other social media usernames, and contact information

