Eligible individuals must (1) have been assigned a male sex at birth and identify as male at the time of enrollment into the study (cis-gender male), (2) be between the ages of 13 and 18 years (inclusive), (3) speak and read English, (4) report same-sex attractions and/or behaviors, (5) have access to the Internet, (6) live in one of the zip codes at least partially contained in the 109 counties included in the four regions selected for this trial, and (7) self-report as HIV-negative at time of enrollment.

Randomization and Blinding

Participants are randomized on a 1:1 basis using a stratified randomization by race and region. AMSM will be randomized to one of two arms, with 300 randomized to each arm (complete data on 250 AMSM per arm, allowing for attrition of 50 AMSM per arm).

Study Assessments

The proposed domains mirror the theoretical framework informing our intervention. We include a summary of the primary and secondary outcomes, key intervention mechanisms of change, and potential covariates. Assessments will not take more than 25 minutes to complete. We have taken several steps to ensure that the assessments are brief and developmentally appropriate. First, AMSM will not answer all listed constructs at every assessment. Identity-related constructs, for example, will be measured at 6-month intervals, whereas other constructs (e.g., comfort discussing sexuality) will be assessed at each follow-up. Second, consistent with best practices that we have used in prior HIV studies with pediatric and adolescent populations^{142,256}, we will use gate-keeping questions to decide whether participants should receive other probes within a domain. For example, a participant who has yet to become sexually active would receive cognitive assessments focused on HIV risk and awareness (e.g., attitudes, norms), but would not receive questions regarding behavioral intentions to engage in HIV prevention in next 3 months (e.g., HIV testing, PrEP) or questions regarding sexual risk behaviors (e.g., sexual behavior, HIV testing, PrEP use). Similarly, at each assessment, AMSM with no lifetime substance use will not be asked about additional substance use questions. Among sexually active participants, gatekeeping also provides opportunities to regulate how detailed the assessments will be.

Domain	Assessment time					
	Baseline	Month 3	Month 6	Month 9	Month 12	Month 15
Primary outcomes						
HIV knowledge	X		X		X	X
Condom use/communication efficacy	X		X		X	X

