HIV/STI testing	X		X		X	X
Outcomes required for analysis						
Demographics	X		X		X	X
Patient provider communication around sexual orientation		X		X		
Stigma		X		X		
Resilience		X		X		
Psychological needs	X		X		X	X
Future life goals		X		X		
Secondary outcomes						
Internalized homonegativity	X		X		X	X
PrEP use and willingness [X		X		X	X
Sex behaviors	X		X		X	X
Substance abuse	X		X		X	X
Depression	X		X		X	X
Anxiety	X		X		X	X
Self-Esteem	X		X		X	X
Covariates						
Peer influence		X		X		
Family support		X		X		
Discrimination		X		X		
Online behaviors		X		X		
Societal reaction to sexual orientation		X		X		
Ethnicity beliefs		X		X		
Relationship history	X		X		X	X
Intervention acceptability		X				

Sample Size

Our expected sample size for analyses across both conditions is N=600 (Intervention, n=300; Control, n=300), assuming a 15-20% loss to follow-up. We estimated the minimum detectable effect sizes at 80% power, for comparisons of the two groups for the continuous primary cognitive (e.g., behavioral intentions, attitudes, norms, self-efficacy) outcomes, as well as the difference in the proportion of AMSM who report increased behavioral in the outcomes (e.g., condom use, HIV testing) to engage in HIV prevention services and behaviors in our treatment arm vs. our attention-control arm. For mean differences, our sample size calculations are based on a two-sample t-test assuming equal variance using a two-sided significance of 0.05. At 80% power, we can detect a between-arm difference of $d=0.22$ at the final follow-up. For repeated measure analyses, assuming a within-person correlation of 0.25, we would be able to detect a difference of 0.08. A less favorable within-person correlation of 0.75 allows us to detect an effect size of 0.11. For proportions, our sample size calculations are based on a two-sample test of proportions using a two-sided significance of 0.05. To have 80% power to compare active treatment to the control group, we require at least 500 participants to find a 12.5% difference between treatment and control in cross-sectional analyses. Assuming within-person correlation of 0.25, we can detect an 8.8% difference. A less favorable within-person correlation of 0.75 allows us to detect an 11.3% difference.

Timing of Analyses

Final analysis will be conducted once the desired sample size is recruited has reached and completed the last study assessment.

Analysis Populations

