Analysis tests the efficacy of the iREACH intervention as compared to a delayed intervention condition, to create positive changes in the following outcomes: *primary outcomes*: changes in confidence to engage in HIV prevention behaviors and changes in HIV knowledge and *secondary outcomes*: changes in sexual behavior and change in HIV testing behavior over the 12-month follow-up period. Descriptive statistics of the behavioral, psychosocial, and demographic characteristics of the participants will be described for all and by group (intervention and control). These will be compared between treatment groups using t-tests or Wilcoxon rank sum tests for continuous variables and chi-square tests for categorical variables. In addition, we will use the general framework of generalized linear mixed models (GLMM) to test for intervention effects over time. Note that some of our outcomes are binary, some count and some continuous traits and thus need to be treated differently. The general form of the GLMM will be $(\mu_{ij}) = \beta_{0i} + \beta_{\text{cov Covariates}_{ij}} + \beta_{\text{Time}_{j}} + \beta_{\text{Intervention Group}_i} + \beta_{\text{Group} \times \text{Time}_i}$, where μ_{ij} is the mean response corresponding to subject i at Time j (baseline and 4 follow-ups) with the appropriate link function (identity for continuous outcome, logit for binary outcome and natural log for count outcomes); Group =1 if the i -th subject is in the intervention group and 0 if the i -th subject is in the attention-control group. The interaction coefficients $\beta_{\text{Group} \times \text{Time}}$ are of interest here, measuring the difference in the rate of change in outcomes across the two treatment groups over time in the primary and secondary outcomes. Models will be compared according to information criterion like AIC, BIC. For some binary outcomes like HIV testing, we will perform an aggregate analysis after collapsing across the repeated measures using simple logistic regression comparing whether the probability of having tested at least once over the entire FU period is different across treatment groups, after adjusting for baseline values. To ensure robustness, we will also apply an exchangeable working correlation structure to its corresponding generalized estimating equation (GEE) model.

Reporting Conventions

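### Race and region stratify the randomisation, but no efficacy model commits to them; the loss is small and conservative, and closing the gap costs nothing

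*SAP*

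**What the plan says.** **Design.** SAP, Randomization and Blinding: "Participants are randomized on a 1:1 basis using a stratified randomization by race and region". The protocol agrees, and its section on assigning subjects to groups (Methods, 3) adds that "Participants recruited nationally will be assigned to a fifth" region. The SAP still describes four regions throughout, and its eligibility criteria still require residence in the counties of those four corridors. Neither document lists the race categories used for stratification.

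**Efficacy models.** SAP, Efficacy Analyses: "we will use the general framework of generalized linear mixed models (GLMM) to test for intervention effects over time". The model has a covariate term, but its contents are not listed there or in the protocol's Statistical Analysis section. The coefficient of interest is Group x Time. The protocol specifies a subject-level random intercept, and the responses run from baseline through four follow-ups. For HIV testing, a logistic regression on ever having tested during follow-up adjusts only for baseline values. The GEE robustness check names no covariates.

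**Where race and region do appear.** The SAP's Covariates and Subgroups section lists race/ethnicity among many variables collected as mediators and moderators, and does not list region. The protocol controls for region in its exploratory social-determinant regressions, and models regional characteristics in a separate two-level analysis.

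**The concern.** When randomisation is balanced within strata that predict the outcome, the between-strata part of the outcome variance no longer contributes to chance differences between arms. An analysis that ignores the strata still counts that variance in its standard error. The test then rejects too rarely under the null and loses some power. Including the strata recovers this with data already in hand.

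The open covariate term raises a second issue. The only schedule of covariates in the SAP is the assessment table, and seven of its eight covariate rows (peer influence, family support, discrimination, online behaviours, societal reaction, ethnicity beliefs, intervention acceptability) have no baseline measurement. They are collected at months 3 and 9, or at month 3 only. An analyst who filled the term from that table would omit the strata and condition on variables that the intervention could change.

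Third, a region factor built from the SAP's four regions would leave national recruits without a value. Under the missing-variable exclusion stated with the per-protocol population, they would drop out of that analysis.

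**Working it through.** **Inputs from the documents.** 250 analysable per arm ("complete data on 250 AMSM per arm, allowing for attrition of 50 AMSM per arm"); a "two-sample t-test assuming equal variance using a two-sided significance of 0.05"; 80% power; d = 0.22; 500 in total for a 12.5-point difference in proportions.

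**Assumed, because the documents give no figure.** Share of outcome variance explained by the strata, R² = 5%, 10%, 20%; 16 strata (20 in two of the checks below); permuted blocks of 4; within-person correlation 0.5.

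**Step 1: the plan's own figures.** With proportions of 0.4375 and 0.5625, n per arm = [1.96√(2 × 0.25) + 0.8416√0.4922]² / 0.125² = 250, so the total of 500 reproduces (reference proportion near 0.5 assumed). For means, detectable d = (1.96 + 0.8416) × √(2/250) = 0.251, not the stated 0.22; power at 0.22 is 69.1%. That mismatch is a separate matter. Power at d = 0.22 is used below only as a common yardstick.

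**Step 2: Group x Time, continuous outcome.** With three assessments, which matches the SAP's schedule for the primary outcomes up to month 12, the within-person slope uses weights (−1/2, 0, 1/2). These sum to zero, so a stratum effect that is constant over time cancels.

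- Fitted random-intercept model, N = 500, R² = 10%: standard error of Group x Time 0.0452 without strata and 0.0452 with strata main effects. With 20% missing at the last visit: 0.0487 and 0.0487.
- A check with five assessments and 20 strata gave estimate 0.02297 and standard error 0.01955, the same with and without strata.
- Simulation, 6,000 runs, no strata against strata-by-time terms, R² = 10%: type I error 0.049 and 0.049; power 68.7% and 68.6%.
- If strata also shift the time trend (slope variance 0.05 on the simulation's scale): type I error 0.044 against 0.049; power 67.0% against 68.7%.

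**Step 3: between-arm comparison of means at month 12, no baseline adjustment.** The true standard error is √(1 − R²) times the one the unadjusted test uses. Hence:

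- actual alpha, unadjusted = 2[1 − Φ(1.96/√(1 − R²))]
- with z = 0.22/√(2/250) = 2.460: power unadjusted = Φ((z − 1.96)/√(1 − R²)); power adjusted = Φ(z/√(1 − R²) − 1.96)
- detectable d, adjusted = 0.2506√(1 − R²)

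| R² | actual alpha, unadjusted | power unadjusted | power adjusted | gain (points) | detectable d, adjusted |
|---|---|---|---|---|---|
| 5% | 0.044 | 69.6% | 71.4% | 1.8 | 0.244 |
| 10% | 0.039 | 70.1% | 73.7% | 3.6 | 0.238 |
| 20% | 0.028 | 71.2% | 78.5% | 7.3 | 0.224 |

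**Step 4: the same comparison adjusted for baseline (simulated).** Power without and with strata: 82.0% and 82.4% at R² = 5%; 81.6% and 82.6% at 10%; 82.2% and 84.3% at 20%. The gains are 0.4, 0.9 and 2.1 points. Type I error without strata was 0.054, 0.044 and 0.044.

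**Step 5: collapsed HIV-testing logistic regression, baseline-adjusted (simulated).** N = 500, 5 regions x 4 race groups, 4,000 runs, strata explaining the stated share of latent variance.

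| Share | type I error without / with strata | power without / with strata | gain (points) |
|---|---|---|---|
| 5% | 0.046 / 0.051 | 76.7% / 78.7% | 2.0 |
| 10% | 0.045 / 0.056 | 75.7% / 78.2% | 2.5 |
| 20% | 0.038 / 0.054 | 68.2% / 73.2% | 5.0 |

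The Monte Carlo standard error of a 5% rate here is √(0.05 × 0.95/4000) = 0.0034, so without strata only the 20% row is clearly below nominal. A second simulation at the same shares gave power of 79%, 76% and 68% without strata against 81%, 79% and 74% with them, gains of 2, 3 and 6 points. The absolute powers depend on the assumed effect and event rate; the differences are what matter.

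**The case against.** The best defence is that nothing is excluded. The mixed model has a covariate term, race/ethnicity is on the SAP's covariate list, and the protocol has a separate analysis that nests participants in regions. The primary continuous outcomes are tested through Group x Time, where stable strata effects cancel. Where the mechanism does operate, the error is on the safe side and the loss is modest. The strata's share of variance is not in the documents, and the disparities cited in the SAP's introduction concern HIV incidence, not HIV knowledge or self-efficacy.

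Most of this stands, and it sets the limits of the point. A reader might infer that the efficacy models leave the strata out, so that the primary test loses precision and has the wrong error rate. The documents do not support that: the strata are unspecified, not excluded, and Step 2 shows practically no effect on the continuous Group x Time test. Nor do they support a fear of false positives, since omission makes the test conservative where it has an effect.

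Three things survive. The collapsed logistic analysis compares levels and names only baseline values. An unlisted covariate term does not pre-specify the strata. The regional two-level model is a separate analysis and puts nothing into the efficacy models. Different time trends by stratum are also possible: the protocol's Background anticipates larger gains in some groups, although that is chiefly effect modification, which is examined separately.

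**Conclusion.** The gap is real and worth closing, but its cost is modest. Neither document commits to race and region in the mixed model, the GEE check or the collapsed logistic regression.

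- **Continuous Group x Time test:** practically no loss, unless the strata predict change over time. In the one scenario with a visible gap, the loss was 1.7 power points.
- **Comparisons of level:** roughly 1 to 6 power points for strata explaining 5% to 20% of variance. For the planned collapsed logistic analysis the range is 2 to 6. The extremes are 0.4 (month-12 mean adjusted for baseline, 5%) and 7.3 (month-12 mean with no baseline adjustment, 20%). Error is at or below nominal within simulation noise.

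These sizes rest on assumed variance shares, numbers of strata, block size and within-person correlation. Repeated-measures models with logit or log links were not simulated; there, adding strata also changes the conditional effect being estimated, which is a further reason to fix the covariates in advance.

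**What to change.** In the SAP's Efficacy Analyses section:

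1. Include the race stratum as used in randomisation and five-level region (four corridors plus national) as fixed effects in the mixed, GEE and collapsed logistic models. List the race categories and say how sparse levels will be combined.
2. Add strata-by-time terms to the longitudinal models, at least as a sensitivity analysis. Main effects alone do not change the continuous Group x Time test.
3. Bring the SAP's four-region definition into line with the protocol's five levels, so that national recruits have a region value.
4. List any other covariates and limit them to values measured at baseline.
5. Adjust for the baseline outcome only where baseline is not already a response. The logistic regression already does so; the mixed model, with baseline among its responses, should not have it added.

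The cost is a few sentences in the SAP. Race, region and the baseline outcomes are already collected. If dropout differs by race or region, having them in the model also makes the missing-at-random assumption behind the likelihood methods easier to defend.
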